## 8. Efficacy assessment

Each day of the study following things will be performed:

a) study drug (glutamine or placebo) will be given intravenously during 12 h.

b) volume of infused solution and time interval of infusion will be registered.

c) total amount of nutrition during 24 h will be recorded.

d) SOFA score will be calculated.

End of ICU-stay will be recorded and as well as the route of discharge. If the patient is moved to another intensive care unit, the patient leaves the study. Still if the patient is treated more than 3 days, he is included and evaluated in the study although the ICU-stay is prolonged in another unit and patient during that time does not receive any controlled treatment. Provision of nutrition after ICU-stay (or after readmission to ICU) will not be recorded. If patient is readmitted to ICU within 24 h study protocol is continued. If patient is readmitted to ICU after more than 24 h the patient will not be included. Patient will not be included again in the study and the second (or consecutive) stay will not be recorded as ICU-stay in the protocol.

#### 8:1 Primary objective

The difference in SOFA-score will be calculated from the day starting nutritional treatment as well as glutamine supplementation until day 7 of ICU stay. For patients discharged or dead before day 7, the SOFA score on the day of discharge/death will substitute the latter score. In case of restrictions in treatment, SOFA score will be recorded as long as the nutrition of the patient is maintained.

## 8:2 Secondary objectives

Mortality in the ICU and after discharge up to 6 months will be recorded and the cause of death will be registered. The difference in SOFA-score will also be calculated until day 10 of ICU stay according to the same procedure as for the primary objective under section 8:1. Length of ICU stay will also be recorded. If the patient is readmitted within 24 h after discharge the study continues. Readmission later than 24 h after discharge will not be recorded.

#### 9. Safety assessment

As administration of the drug is in accord with clinical practice, documentation of safety will not be a primary or secondary objective of the study. Nevertheless as mortality and morbidity are the objective of the study, events characterised as adverse events or serious adverse events will be recorded and reported.

#### 9:1 Adverse event

In the study any event, regardless if there is any suspected connection to the study drug or not, that requires treatment and that is not reflected in the SOFA score, will be recorded as an adverse event. The investigator's concerning possible relation to the study drug will be noted.

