#### 9:2 Serious adverse event

All deaths occurring in patients randomised in the study will be reported as serious adverse events, using the specific form. The study monitor should be contacted within 24 h and a signed copy of the form should be faxed to the monitor within 5 working days.

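### Section 9:1 keeps any event reflected in SOFA out of adverse event recording even when the study drug is suspected, and 9:2 gives no prompt-report route for non-fatal cases

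*Protocol*

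**What the plan says.** Section 9 of the protocol treats safety as secondary to efficacy: "documentation of safety will not be a primary or secondary objective of the study". It still commits to some recording, because "events characterised as adverse events or serious adverse events will be recorded and reported". It does not define either term; the two subsections do that work.

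Section 9:1 sets the scope of an adverse event. It starts from "any event, regardless if there is any suspected connection to the study drug or not", and then keeps only an event "that requires treatment and that is not reflected in the SOFA score, will be recorded as an adverse event". The same section provides for causality: the investigator's view "concerning possible relation to the study drug will be noted".

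Section 9:2 deals with serious events and names one category: "All deaths occurring in patients randomised in the study will be reported as serious adverse events, using the specific form". The notification rule follows directly: "The study monitor should be contacted within 24 h", with a signed form to follow within 5 working days.

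Appendix 19:1 shows what the SOFA score reflects: oxygenation ratio, platelets, bilirubin, blood pressure or vasoactive drugs, Glasgow Coma Scale, and creatinine or urine output. Section 8 has the score calculated each day.

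**The concern.** There is a good reason for not reporting every SOFA change as an adverse event. Organ failure is common in intensive care, and here it is the primary outcome. The difficulty is that the exemption makes no exception for suspected drug reactions. The clause on suspected connection means that suspicion has no bearing on whether an event qualifies, so the SOFA exclusion applies equally to a deterioration the investigator blames on the underlying illness and to one he or she blames on the infusion.

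What is lost is the investigator's causality judgement at the time of the event, and any prompt notice to the monitor when the patient survives. A judgement that was never asked for cannot be recovered in the analysis. At the end of a trial planned for 1,000 patients, the report could not state how many SOFA-reflected organ events were suspected to be drug-related. Section 14 gives the lack of a double-blind, placebo-controlled, multi-centre evaluation in intensive care patients as the reason for the trial, so this count is one that readers would reasonably want.

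**Working it through.** No arithmetic applies. The check is to apply the definitions to each type of event, and then to look for any other place in the protocol that would catch what they miss.

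**Step 1. The conditions.** Under 9:1 an event must (i) require treatment and (ii) not be reflected in SOFA. Both must hold, and suspicion of the drug changes neither. The relatedness note is provided for only within 9:1, so it attaches to events that already qualify. Under 9:2 the form and the 24 h contact attach to deaths; no non-fatal category is named there or elsewhere.

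**Step 2. Four cases.**

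| Event | Adverse event (9:1)? | Relatedness noted? | Form and 24 h contact (9:2)? |
|---|---|---|---|
| (a) Non-fatal, drug suspected, reflected in SOFA | No | No | Not named |
| (b) Non-fatal, drug suspected, treated, not reflected in SOFA | Yes | Yes | Not named |
| (c) Fatal | Covered by 9:2 | Not stated in 9:2 | Yes |
| (d) Non-fatal, needing no treatment | No | No | Not named |

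Case (a) is the point made here. An example is a rise in creatinine or bilirubin that crosses a SOFA threshold and that the investigator attributes to the infusion.

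**Step 3. Other routes for case (a).**

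- Section 8, daily SOFA: the deterioration is scored, without a statement of cause.
- Section 6:4: a reason is recorded, but only if participation is terminated.
- Appendix 19:4: the discharge form offers withdrawn consent, failed drug administration or another reason, and only for a drop-out.
- Section 13: the check after 200 patients concerns whether the protocol works and recruitment is adequate. The look after 500 patients concerns the primary endpoint.
- Sections 8:1 and 8:2: the planned SOFA comparisons are changes from start to day 7 and day 10. Section 7 continues treatment for the whole ICU stay, so an injury that resolves before those days, or begins after day 10, need not appear in either comparison.

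None of these produces an event record, a causality judgement or a prompt notice for a patient who stays in the trial and survives.

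**The case against.** The strongest reply is that this is a reasoned choice. Section 9 explains that the product is given in line with ordinary practice and that morbidity is itself the outcome. Reporting expected organ failure a second time as adverse events would add work and little information. The score is calculated daily, reported electronically (sections 5:4, 11 and 15:1) and compared between arms at the 500-patient look, where continuation is decided. An investigator with a suspicion may end participation and record why. Section 3 reports no adverse reactions in earlier studies of the dipeptide.

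Much of this stands, and it rules out several stronger readings that a reader might infer:

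- **That all six SOFA organ systems are outside adverse event recording.** The exemption covers events reflected in the score, not organ systems. SOFA uses narrow markers, so a treated arrhythmia, a seizure that leaves the coma score unchanged, or a bleed with normal platelets is still an adverse event with relatedness noted.
- **That harm could not be seen or acted on.** An excess of organ dysfunction in one arm can be measured through the daily scores and the interim comparison.
- **That the exempted organs are those most at risk from the drug.** Nothing in the protocol identifies expected sites of harm.
- **That organ-level information is lost inside a total score.** The total is built from components, and only the discharge part of the report form is shown, so whether components are kept separately cannot be judged. How to tabulate them is a matter for the analysis plan.
- **That 9:2 rules out non-fatal serious events.** It does not say that deaths are the only category. It names no other, and neither does any other section.

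What the reply does not answer is the suspected case. Avoiding duplicate reports of expected organ failure justifies exempting events thought unrelated. It gives no reason to exempt those the investigator attributes to the infusion. Nor is this a detail left to a later plan: 9:1 states the rule, mentions suspected connection expressly, and governs what sites write down.

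**Conclusion.** The point holds in a limited form. Followed exactly, 9:1 and 9:2 leave a non-fatal, SOFA-reflected, drug-suspected deterioration with no individual event record, no relatedness judgement and no stated prompt notice. It survives only as points in the daily score, which supports a comparison by arm but not a count of suspected reactions.

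The number of such events cannot be derived from the protocol, which gives no expected rate, and none is assumed here. The conclusion rests on two readings: that the conditions in 9:1 apply jointly, as the sentence is built, and that a category named nowhere has no stated reporting route. Forms not shown in the protocol might in practice ask for more, but the text does not require it. The point does not affect the primary endpoint, the sample size or treatment. It is a correction that should be made, because the lost information bears on patient safety and cannot be reconstructed later.

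**What to change.** **Section 9:1.** Limit the SOFA exemption to events that the investigator does not suspect are related to the study drug. Any suspected event is then recorded as an adverse event, with relatedness noted, whether or not SOFA reflects it. Unrelated organ failure stays exempt, so the purpose of the exemption is kept. The sentence should also make clear whether a suspected event that needed no treatment is included, since the treatment condition is separate from the SOFA condition.

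**Section 9:2.** Extend the existing form and the 24 h contact from deaths to non-fatal serious events suspected to be related, and state what counts as serious in a survivor, since the protocol has no such definition.

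**Cost.** About one sentence in each section, use of the form that already exists, and a few additional forms for suspected cases. Endpoints, sample size and treatment are unchanged.

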#### 9:2 Serious adverse event

All deaths occurring in patients randomised in the study will be reported as serious adverse events, using the specific form. The study monitor should be contacted within 24 h and a signed copy of the form should be faxed to the monitor within 5 working days.

#### **10. Statistics**

The study is designed with one primary endpoint as the primary objective and several secondary endpoints as secondary objective. The statistical power calculation to determine the sample size is performed for the primary endpoint. Parametric and non-parametric statistics will be used depending on whether the parameters are normally distributed or not. As 3 days of treatment is an inclusion criteria all calculation will be made on included as well as randomised patients (intention to treat)

#### 10:1 Primary objective

The change in SOFA score between day of start of treatment and day 7 of ICU stay will according to historical data be normally distributed, and therefor the groups will be compared using parametric statistics (Student's t-test). As the primary endpoint will be used in the planned interim analysis after inclusion of 500 patients, an adjustment for the level of significance will be performed accordingly.

#### 10:2 Secondary objectives

The 6-months mortality will be recorded from the public register. Mortality rates will be compared using a Kaplan-Meyer plot and ?-analysis. The change in SOFA score will be compared between groups using Student's t-test, as for the primary end-point.

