Another problem is how to define morbidity and mortality. The latter is easily defined although the ICU mortality may be influenced by different routines in individual centres. In addition the beneficial effects attributable to nutritional support may be extended also to the convalescence and rehabilitation period and therefore 6-months mortality is considered a more adequate measurer than in unit or in hospital mortality. Concerning morbidity it may be reflected in the SOFA-score, which take failure in several organs into account (38). As there is a close correlation between SOFA-score and mortality, it may be the best integrated measure of morbidity. Morbidity of clinical importance it may also be reflected in the length of ICU-stay. It is obvious that ICU-stay is variable inbetween units as much as it depends upon the pressure on available ICU-beds and the quality of the post-ICU care. Hospitals with step down units may have quite different routines from those hospitals that lack such a facility. Although there will be considerable differences between units, a block-randomisation may at least to some extent take care of these problems. Still definition of morbidity is problematic, and to choose a measure of morbidity as a primary endpoint must always include a number of compromises.

In addition a close record of the nutrition given is also necessary to verify that the intended treatment is actually received by the patients. The record should include the energy given as well as nitrogen content.

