### 6:1 Screening

Screening will be performed when it is decided to prescribe full nutrition to the patient, usually during the initial 2 days of ICU-stay before the trial starts. During the screening following tasks will be performed.

- a) Detailed patient/relative information by the investigator and handout of the written patient/relative information
- b) List of inclusion/exclusion criteria will be checked
- c) Subject's demographic data will be controlled

Recording of APACHE II score at admission (during first 24 h of stay)

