#### 6:2 Inclusion criteria

Subjects will be enrolled in the trial when they meet the following criteria:

- a) admission to the ICU
- b) decision to give the patient full nutrition
- c) APACHE II score >10 at admission
- d) age 18-85 years

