#### 6:5 Randomisation

Subjects will be randomised to treatment only if they satisfy all inclusion criteria. The trial will include 500 subjects in each treatment group. Block randomisation means that the subjects will be assigned randomly to active or placebo treatment with equal size of the two treatment groups at each investigational centre. A computer program using the method of random allocation within fixed blocks will generate a randomisation list. It will provided for a defined number of subjects and a defined number of reserve subjects at each investigational centre. The randomisation list will be securely locked away during the trial by the responsible statistician until clean file has been declared.

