#### 10:5 Statistical methods

Student's t-test will be used to compare the 2 groups when variables are normally distributed, this is expected to be the case for the change in SOFA score. For length of stay a rank-test will be used where survival is ranked higher than death and death after a long period of time is ranked higher than death after a short period of time. For mortality a Kaplan-Meyer plot and ?-analysis will be used.

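### The mortality comparisons in 10:2 and 10:5 are unadjusted, although APACHE II and age are known before treatment for every eligible patient: a modest loss of efficiency, not a bias

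*Protocol*

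**What the plan says.** **Test.** Protocol section 10:2 says "Mortality rates will be compared using a Kaplan-Meyer plot and" an analysis whose symbol was lost when the PDF was read (a query mark followed by a superscript 2). Section 10:5 repeats it: "For mortality a Kaplan-Meyer plot and" the same analysis. Neither section names a covariate or stratification factor for mortality, and no other section does.

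**Endpoints.** ICU and 6-month mortality are secondary (4:2). The Background nevertheless ranks them: "6-months mortality is considered a more adequate measurer than in unit or in hospital mortality". On size, section 10 states "The statistical power calculation to determine the sample size is performed for the primary endpoint", which is the change in SOFA score.

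**Baseline data.** Section 6:2 requires "APACHE II score >10 at admission" and "age 18-85 years". Section 6:1 has APACHE II recorded at screening, from the first 24 hours of the stay. Under 6:5 only patients who meet all inclusion criteria are randomised.

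**Balance.** Section 6:5 allocates in fixed blocks, "with equal size of the two treatment groups at each investigational centre". Neither severity nor age is a balancing factor.

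**The concern.** Eligibility covers a wide spread of baseline risk: 67 years of age (85 − 18) and any APACHE II score above 10. A severity score and age can be expected to predict death in such a population. Both values are measured before treatment and are complete by construction, so using them requires no new data.

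Mortality precision is whatever about 1,000 patients provide, because the sample size was set for SOFA. An unadjusted test leaves the variation explained by severity and age in the error term, and leaves any chance difference in severity between arms in the estimate. At stake is some power for the mortality endpoints, including the one the Background prefers.

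**Working it through.** **The plan's own figure.** There is none for mortality. The approximately 500 per group in 10:3 is for a 0.75-point SOFA difference and does not bear on this point.

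**Inputs.** From the protocol: 500 per arm, 1:1 (6:5). Assumed, because the protocol does not give them: two-sided 5% level; control mortality 30% (also 20% and 40%); an absolute reduction of 8 points (also 4); and an AUC of about 0.63 to 0.75 for APACHE II and age together.

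**Step 1: unadjusted power.** For two proportions with n per arm and p̄ their mean,

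power = Φ{ [ |p₁ − p₂| − 1.96·√(2p̄(1 − p̄)/n) ] / √[(p₁(1 − p₁) + p₂(1 − p₂))/n] }.

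With 0.30, 0.22, p̄ = 0.26 and n = 500:
- pooled SE = √(2 × 0.26 × 0.74/500) = 0.02774
- unpooled SE = √((0.2100 + 0.1716)/500) = 0.02763
- power = Φ[(0.08 − 0.05437)/0.02763] = Φ(0.928) = 82.3%

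The same formula gives 93.3% for 20% against 12% and 75.1% for 40% against 32%.

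**Step 2: power with adjustment.** Three simulations compared the chi-square test with the treatment coefficient of a logistic model that includes the baseline predictors. All use 30% against 22% and 500 per arm.
- A: 3,000 trials per setting; APACHE II drawn from N(20, 7) truncated at 11 or more, age from N(60, 15) truncated to 18–85.
- B and C: 2,000 trials per setting; one baseline risk score standing for both variables.

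| AUC, about | A | B | C |
|---|---|---|---|
| 0.63 | 80.9 → 82.5% | 82.7 → 84.5% | 82.2 → 83.4% |
| 0.70 | 83.8 → 86.8% | 83.0 → 86.9% | 81.5 → 85.7% |
| 0.75 | 82.3 → 87.7% | 82.1 → 88.5% | 83.2 → 88.5% |

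The gains are 1.2–1.8, 3.0–4.2 and 5.3–6.4 points. The unadjusted column should be constant at 82.3%. Its scatter is simulation error: √(0.82 × 0.18/3,000) = 0.7 points for A, and √(0.82 × 0.18/2,000) = 0.9 points for B and C.

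At other control rates with an 8-point reduction, B gives 94.2 → 95.7% and 92.4 → 95.4% (control 20%, AUC 0.70 and 0.76), and 74.1 → 78.8% and 77.6 → 85.5% (control 40%, same AUCs).

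**Step 3: validity.** With no treatment effect, both tests rejected in about 4–6% of trials in B and 4.4–5.2% in C, which is nominal within simulation error.

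**Step 4: a smaller effect.** In A, adjustment is worth sample-size ratios of 1.045, 1.091 and 1.169. For 30% against 26%, Step 1 gives 29% power at n = 500. Multiplying n by the three ratios gives 30%, 31% and 33%.

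**Step 5: chance imbalance.** The standard error of a standardised baseline difference is √(2/500) = 0.063. In C, the resulting difference in baseline risk between arms had an SD of 0.65, 0.9 and 1.2 percentage points at the three AUCs. The 95% range is therefore about ±1.3 (1.96 × 0.65) to ±2.4 (1.96 × 1.2) points.

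**The case against.** **The unadjusted test is valid.** This stands in full. Under 1:1 randomisation it is unbiased and holds its error rate, which already allows for chance imbalance. A reader might infer that the planned comparison is biased or anti-conservative. Neither the documents nor the calculation supports that.

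**The test may not be a chi-square of proportions.** This also stands. Placed beside a Kaplan-Meier plot, the garbled term could mean a log-rank chi-square. A reader might take the crude-proportions reading as certain, but the text does not settle it. The point survives because both tests are unadjusted. If log-rank was meant, a logistic model would not use event timing, which is a reason to keep the survival analysis as support. The gains above are measured against the chi-square test.

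**The size rests on assumptions.** True. Eight points is a large effect for a trial that says it considered a limited one (10:3), and at four points the absolute gain is only 1 to 4 points. ICU mortality has no separate calculation. B and C fit the model that generated the data, which favours adjustment.

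**An SAP may deal with it.** It could add an adjusted analysis, and the protocol does not forbid one. But the protocol names the unadjusted method twice, so making an adjusted analysis the main one would depart from its text.

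**An adjusted odds ratio and a risk difference are different analyses.** Correct: testing one and reporting the other could give a p-value and an interval that disagree. The fix therefore takes both from one estimate.

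**Conclusion.** The point holds as one of efficiency. Sections 10:2 and 10:5 fix an unadjusted comparison of ICU and 6-month mortality, although two likely predictors of death are in hand for every eligible patient and are not balanced by design.

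If mortality is 30% against 22%, with 500 per arm and a two-sided 5% level, adjustment is worth about 1–2 points of power at AUC 0.63, 3–4 at 0.70 and 5–6 at 0.75. None of these inputs except the arm size comes from the documents. The direction was the same in every scenario shown; the size depends on how well APACHE II and age predict death in this population.

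It would be too strong to conclude that adjustment makes the trial adequately powered for mortality. At 30% against 26%, power stays at about 30% with or without it. The change is worth making because it costs almost nothing, not because the planned analysis is invalid.

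**What to change.** In 10:2 and 10:5, prespecify the main comparison of each mortality endpoint as follows:
- a logistic regression of death on treatment, with APACHE II and age as continuous covariates;
- the intention-to-treat population already defined in 10:6;
- the effect reported as a standardised (marginal) risk difference, with the 95% confidence interval and the p-value both taken from that estimate.

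Centre, the blocking factor, may be added as a stratum where numbers per centre allow. Keep the Kaplan-Meier plot and the unadjusted test as supportive analyses, and state whether that test is a chi-square of proportions or a log-rank test.

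The cost is a sentence or two in each section and a slightly less simple analysis of secondary endpoints. No data collection is added, and the effect stays on the absolute scale of the crude comparison. The change should be made before unblinding, so that the choice of covariates cannot be disputed if the arms turn out to differ in severity.
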